#### **4.2.2. Part B: 104-week extension phase**

All subjects who complete Part A of the study will be eligible to enter part B. The two populations of subjects expected to enter into Part B are:

- Subjects in remission at the primary 52-week endpoint. These subjects will discontinue blinded study drug treatment on entry into Part B and will be followed for maintenance of response. However, in the event of a flare, they will have the option to receive, at the discretion of their Investigator, open-label sirukumab 100 mg SC q2w for a maximum of 52 weeks during the first 52 weeks of Part B.
- Subjects not in remission, at the primary 52-week endpoint or subjects who have not been able to taper prednisone during Part A. Upon entry into Part B, these subjects will have the option to receive, at the discretion of the Investigator, open-label sirukumab 100 mg SC q2w for a maximum of 52 weeks.

For subjects who newly flare at any time during the 1st 52 weeks of Part B and require a treatment change, open-label sirukumab 100 mg SC q2w can be initiated within the first 52 weeks of Part B. The duration of treatment will be at the discretion of the investigator but must not exceed 52 weeks. Treatment with open-label sirukumab 100 mg SC q2w must complete by Week 104 (the end of the extension phase). Corticosteroid use or the initiation of methotrexate therapy alone or in addition to sirukumab treatment during Part B will be at the discretion of the investigator.

Treatment with open-label sirukumab 100 mg SC q2w must complete by Week 104 (the end of the extension phase). Adjustments in corticosteroid dose or the initiation of methotrexate therapy alone or in addition to sirukumab treatment during Part B will be at the discretion of the investigator.

Investigators should carefully consider the individual benefit-risk of continuing sirukumab in those subjects that continue to experience flares or persistent disease activity following the start of open label treatment.

Upon **study** completion, decisions on treatment options for individual subjects will be at the discretion of the investigator.

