#### 4.6.1. Risk Assessment

Potential Risk of Clinical Significance	Summary of Data/Rationale for Risk	Mitigation Strategy
Investigational Product (IP) [sirukumab]		
TB reactivation	Cases of TB reactivation have been reported with IL-6 antagonists, such as tocilizumab and sirukumab.	Inclusion only of subjects with no evidence of active or latent TB infection, negative diagnostic TB test at Screening and Screening chest radiograph showing no evidence of current or previous pulmonary TB (Section 5.1 Bullet 4). Evaluation of TB throughout the study by use of a TB questionnaire and a TB test (Section 7.5.7)
Serious/opportunistic infections	IL-6 deficient mice have been noted to be susceptible to infections with Listeria , monosytogenes , Toxoplasma gondii , and Candida albicans [Dalrymple, 1995; Romani, 1996; Suzuki, 1997]. Serious, life-threatening infections such as septic shock, some of which have been fatal, have occurred in subjects receiving sirukumab.	Exclusion of subjects with an active current or history of recurrent bacterial, viral, fungal, mycobacterial, or other infection or those with a prior episode of major infection (serious infectious event). Monitoring of serious and opportunistic infections by IDMC.
Hypersensitivity	Serious allergic reactions (eg, anaphylaxis) have been reported with the administration of mAbs, including sirukumab, and may occur during or after the administration of the mAbs.	Exclusion of subjects with severe allergic reactions to monoclonal antibodies, human proteins, or excipients. Subjects will be made aware of the potential risk, the signs and symptoms of such reactions, and the importance of immediately seeking medical attention. Discontinuation of blinded subcutaneous study drug in the event of a severe allergic reaction. Monitoring of serious allergic reactions by IDMC; adjudication and classification of these events using Sampson criteria (Sampson, 2006) by

Potential Risk of Clinical Significance	Summary of Data/Rationale for Risk	Mitigation Strategy
		sponsor safety review team will be implemented.

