Gastrointestinal perforation	Upper and lower GI tract perforations occurred in the anti-IL-6 receptor (tocilizumab) & the anti-IL6 (sirukumab) Phase III programs. Sirukumab binds to IL-6 and prevents binding to IL-6 receptor (IL-6R). Tocilizumab binds to IL-6 R to prevent IL-6 signalling. Potential differences in safety between agents that bind to the IL-6 receptor versus ones that bind to the IL-6 ligand (sirukumab) warrants further study.	Exclusion of subjects with a history of diverticulitis, inflammatory bowel disease, or other symptomatic GI tract condition that might predispose to bowel perforation. Investigators should closely monitor for GI perforations with a high degree of suspicion. Monitoring of gastrointestinal perforations by IDMC.
Cytopenias	Neutropenia and thrombocytopenia have occurred in sirukumab studies, including severe thrombocytopenia associated with bleeding. Most patients who developed neutropenia while being treated with sirukumab did not develop infections, and most patients who developed thrombocytopenia did not experience bleeding events. Decreases in platelet counts have also been observed.	Exclusion of subjects with absolute neutrophil count (ANC) $<2 \times 10^9/L$ , platelet count $<140 \times 10^9/L$ , WBC count $<3.5 \times 10^9/L$ , ALC $<0.5 \times 10^9/L$ . Discontinuation of blinded subcutaneous study drug for subjects with 2 confirmed consecutive absolute neutrophil counts of $<0.5 \times 10^9$ cells/L or platelet counts $<50 \times 10^9$ cells/L. Monitoring of cytopenias by IDMC.
Lipid increases	Increases in blood total cholesterol, LDL, HDL, and triglycerides have occurred in sirukumab-treated subjects. No dose response was observed.	Monitor HDL/LDL levels, administer a cholesterol lowering agent if indicated.
Liver enzyme increases	Transient asymptomatic increases (1 to 3 x ULN, sometimes $> 5 \times$ ULN but $< 8 \times$ ULN) in blood ALT and AST values have been observed in subjects in completed and ongoing studies of sirukumab. Six subjects have had ALT or AST $>3 \times$ ULN and bilirubin $>2 \times$ ULN; all 6 had received	Exclusion of subjects with AST or ALT $>2.0 \times$ ULN, or total bilirubin $>ULN$ with the exception of Gilbert's disease. Inclusion of pre-defined liver chemistry discontinuation criteria (Section 5.4.3). Monitoring of hepatic abnormalities by IDMC.

Potential Risk of Clinical Significance	Summary of Data/Rationale for Risk	Mitigation Strategy

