## 7. STUDY ASSESSMENTS AND PROCEDURES

Protocol waivers or exemptions are not allowed with the exception of immediate safety concerns. Therefore, adherence to the study design requirements, including those specified in the Time and Events Tables, are essential and required for study conduct.

This section lists the procedures and parameters of each planned study assessment. It should be noted that for those subjects with disease flare at any visit, the assessments to

be performed are those specified in the Early Withdrawal or Flare visit in all of the following Time and Events Tables.

The assessments for Part A of the study are provided in Time and Events [Table 2](#) in Section [7.1](#).

Part B assessments are included in separate Time and Events Tables ([Table 3](#), [Table 4](#) and [Table 5](#)). It should be noted that the Week 52 visit of Part A also serves as the Week 0 visit of Part B of the study.

Part B Time and Events Tables should be followed as described below:

Time and Events [Table 3](#): Assessments for subjects who will **not** receive open-label treatment with sirukumab during Part B. Dispensing of investigational product is not required. Hematology and clinical chemistry assessments and pregnancy testing from the Week 16 visit onwards are also not required as subjects will have completed the 16-week post-drug follow up assessments.

Time and Events [Table 4](#): Assessments for subjects who initiate open-label sirukumab treatment **at** the baseline visit of Part B (those with disease activity or flare at the Week 52 visit of Part A).

Time and Events [Table 5](#): Assessments for subjects who initiate open-label sirukumab treatment **after** the baseline visit and anytime up to the Week 52 visit of Part B (those who flare during Part B). These subjects will initially be following the assessments in Time and Events [Table 3](#) and will undergo the assessments scheduled for that visit and will include initiation of open-label sirukumab treatment at that same visit.

Subsequent visits will follow the assessments from Time and Events [Table 5](#) starting from the visit labelled 'plus 2 weeks' onwards. It is important that upon initiation of open-label sirukumab therapy, the next visit should occur **2** weeks after treatment start. For these subjects, the last visit in Part B should be scheduled for when they have been in Part B for 104 weeks or upon completion of the 16-week follow-up if applicable.

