Exploratory Lab Assessments												
IL-6 measurements	x											
Blood Biomarkers & exploratory markers	x											
Blood and Urine Markers, Transcriptomics (optional)	x											
Exploratory US Imaging												
Ultrasound imaging 											x	

1. Assessment from Week 52 visit of Part A
2. PROs to be completed by subjects before other clinically evaluated assessments or blood draws and before the administration of study drug. At visits where subject is fasting for blood draws, the option exists to perform blood draws prior to completing PROs as necessary to end the fast. HAQ-DI administered only to sub-set of subjects with PMR. PGA assessed using PtGA (subjects) and PhGA (physicians, after subject completion of questionnaires and after conducting patient assessments).
3. Brief physical exam.
4. Measure in a semi-supine position after 5 minutes rest; includes blood pressure, temperature and heart rate.
5. Suggested questions (see Section 7.5.7). A QuantiFERON-TB Gold Test should be performed at any time during the study if TB is suspected.
6. To be performed only if Early Withdrawal visit or flare occurs on or before Week 16 visit.
7. Pregnancy test: urine = U, serum = S. Premenopausal women only.
8. For subjects participating in the exploratory US imaging cohort. Ultrasound scans to be performed only in the event of disease flare or relapse in Part B. Part B scans will conclude when the last subject in the US imaging cohort completes Part A.

**Table 4 Time and Events Table for Part B (104-week Extension) of the Study: Subjects Receiving Open-label Sirukumab Immediately Upon Entry into Part B**

	Wk 0/(Wk 52 of Part A)	Wk 2±5d	wk 4±5d	wk 8±5d	wk 12±5d	wk 16±5d	wk 24±5d	wk 36±5d	wk 48±5d 	wk 52±5d	wk 76±5d	wk 104±5d	Flare	Early Withdrawal	Follow Up
Dispense Investigational Product	x	x	x	x	x	x	x	x	x						
Assess Invest. Product compliance	x	x	x	x	x	x	x	x		x			x	x	
Concomitant Medications	x	x	x	x	x	x	x	x		x	x	x	x	x	x
Efficacy Assessments															
GCA disease activity	x	x	x	x	x	x	x	x		x	x	x	x	x	
PGA (patient, physician) 	x	x	x	x	x	x	x	x		x	x	x	x	x	
Health Outcomes															
Pain NRS 	x	x	x	x	x		x			x	x	x	x	x	
HAQ-DI 	x				x		x			x	x	x	x	x	
FACIT-Fatigue 	x				x		x			x	x	x	x	x	
Steroid Impact 	x				x		x			x	x	x	x	x	
SF-36v2 (acute) 	x				x		x			x	x	x	x	x	
EQ-5D (5L) 	x				x		x			x	x	x	x	x	

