Serum chemistry		X	X	X	X	X	X	X		X	X	X	X	X	

	Start of open-label sirukumab 	PLUS 2 Wks±5d	PLUS 4 Wks±5d	PLUS 8 Wks±5d	PLUS 12 Wks±5d	PLUS 16 Wks±5d	PLUS 24 Wks±5d	PLUS 36 Wks±5d	PLUS 48 Wks±5d 	PLUS 52 Wks±5d	PLUS 76 Wks±5d	PLUS 104 Wks±5d 	Flare	Early Withdrawal	Follow Up
CRP		x	x	x	x	x	x	x		x	x	x	x	x	
ESR		x	x	x	x	x	x	x		x	x	x	x	x	
Lipid panel (fasting)					x	x	x	x		x	x	x	x	x	
Hemoglobin A1c					x	x	x	x		x	x	x	x	x	
Pregnancy Test 			U	U	U	U	U	U	U	U	U	U		U	U
PK 					x					x		x	x	x	x
Immunogenicity 					x					x		x	x	x	x
Exploratory US Imaging															
Ultrasound imaging 													x		

1. Upon the initiation of open-label sirukumab, perform the assessments from Time and Events [Table 3](#) at the visit the subject was scheduled to undergo when study drug is started.
2. Visit only to dispense IP; no assessments are required.
3. Although this visit is labelled as 104 weeks since the start of open-label sirukumab, it does not take into account the exact start time, since this will be different for each subject depending upon when in the first 52 weeks of Part B open-label sirukumab was started. The important point to note, is that this last visit should be scheduled when each of these subjects will complete 104 weeks in Part B.
4. PROs to be completed by subjects before other clinically evaluated assessments or blood draws and before the administration of study drug. At visits where subject is fasting for blood draws, the option exists to perform blood draws prior to completing PROs as necessary to end the fast. HAQ-DI administered only to sub-set of subjects with PMR. PGA assessed using PtGA (subjects) and PhGA (physicians, after subject completion of questionnaires and after conducting patient assessments). .
5. Brief physical exam.
6. Measure in a semi-supine position after 5 minutes rest; includes blood pressure, temperature and heart rate.
7. Suggested questions (see Section [7.5.7](#)). A QuantiFERON-TB Gold Test should be performed at any time during the study if TB is suspected.

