Only demographic and baseline characteristic as well as Safety will be displayed for Part B. All demographic and baseline characteristic as well as Safety summaries produced for Part A will be produced for Part B. Part B outputs will be displayed using the same general layout of Part A outputs, using the same Part A group as the treatment groups.

Each output will be split using a by-line which will contain information on Part B:

- “Never Received OL Sirukumab during Part B” will include all subjects who did not take a dose of Received OL Sirukumab during Part B.
- “Received at Least 1 Dose of OL Sirukumab during Part B” will include all subjects who took at least one dose of OL Sirukumab during Part B.

The Baseline for Part B will be the last measurement done up to and including the Week 52 visit date of Part A.

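### Subjects who start open-label sirukumab after Part B Week 16 have no haematology, chemistry or TB evaluation scheduled at the start visit

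*Protocol*

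**What the plan says.** Protocol Section 4.2.2 says that, for a new flare, "open-label sirukumab 100 mg SC q2w can be initiated within the first 52 weeks of Part B". Section 7 explains how the start visit works: a subject who has been following Table 3 "will undergo the assessments scheduled for that visit and will include initiation of open-label sirukumab treatment at that same visit". Footnote 1 of Table 5 repeats this, sending the subject to the Table 3 assessments "at the visit the subject was scheduled to undergo when study drug is started". Table 5 takes over only from its PLUS 2 weeks visit.

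On Table 3, Section 7 states that "Hematology and clinical chemistry assessments and pregnancy testing from the Week 16 visit onwards are also not required", because the 16-week off-drug follow-up is complete by then. The flare and early-withdrawal entries for haematology, chemistry, lipids and HbA1c carry footnote 6: "To be performed only if Early Withdrawal visit or flare occurs on or before Week 16 visit".

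The risk table in Section 4.6.1 names as mitigation for TB reactivation "Evaluation of TB throughout the study by use of a TB questionnaire and a TB test". On blood counts it records that "Neutropenia and thrombocytopenia have occurred in sirukumab studies, including severe thrombocytopenia associated with bleeding".

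SAP Section 11 says: "The Baseline for Part B will be the last measurement done up to and including the Week 52 visit date of Part A". SAP Tables 11 and 13 repeat the protocol schedules.

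**The concern.** The reason for stopping the tests at Week 16 fits a subject who stays off drug. It does not fit one who is about to be dosed. Read together, the rules let a subject start or restart sirukumab between Weeks 16 and 52 with no scheduled check on blood counts, liver enzymes or TB at that visit.

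Two things are at stake.

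- **Safety.** Protocol Table 7 requires sirukumab to be interrupted at ANC of 1.0 x 10^9/L or less, platelets of 100 x 10^9/L or less, or ALT/AST of at least 3 x ULN. A late starter could already meet one of these limits at the first open-label dose with no scheduled test to show it. Methotrexate may have been added in the meantime at the investigator's discretion. For someone from Arm D or E it is the first sirukumab exposure.
- **Interpretation.** With nothing scheduled between Week 16 and the start, an abnormal value at PLUS 2 weeks may reflect the drug or may have arisen before the first dose; the data cannot say which. The SAP baseline is the Part A Week 52 value, which in Arms A to C is normally taken on sirukumab, so it is not an off-drug reference for these subjects either.

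**Working it through.** The plan states no figure for this point, so the check sets the grids side by side and computes the age of the last scheduled values.

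**1. What is marked at each kind of start visit**

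| Assessment | Table 4 (start at Part B entry) | Table 3, Weeks 24, 36, 52 | Table 3, Flare column | Table 5, Start column |
|---|---|---|---|---|
| Haematology, chemistry | yes | blank | only to Week 16 | blank |
| Lipids, HbA1c | yes | blank | only to Week 16 | blank |
| TB evaluation | yes | blank | blank | blank |
| Pregnancy test (premenopausal only) | yes | blank | blank | blank |
| C-SSRS | yes | blank | yes | yes |
| GCA activity | yes | yes | yes | yes |

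A flare visit after Week 16 still has physical examination, vital signs, adverse events, C-SSRS, CRP and ESR.

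**2. Age of the last scheduled values** = start week minus 16, the last Table 3 week marked for haematology, chemistry and TB evaluation.

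- Week 24: 24 - 16 = 8 weeks (46 to 66 days with the 5-day windows at both visits)
- Week 36: 36 - 16 = 20 weeks (130 to 150 days)
- Week 52: 52 - 16 = 36 weeks (242 to 262 days)

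Section 7, read literally, drops haematology and chemistry at Week 16 itself, which conflicts with the marks in Table 3. On that reading the last values are from Week 12 and the ages are 12, 24 and 40 weeks, so the figures above are the smaller ones. A flare at an unscheduled visit between Weeks 16 and 52 gives an age between 0 and 36 weeks.

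**3. Share of the initiation window.** Table 3 visits after Week 0 up to Week 52 are 4, 8, 12, 16, 24, 36 and 52, seven in all. Three of the seven (24, 36, 52) lack the tests.

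**4. Yardstick from the plan itself.** Table 5 has haematology at PLUS 2, 4, 8, 12, 16, 24, 36 and 52 weeks. The intervals are 2, 4, 4, 4, 8, 12 and 16 weeks, so the longest gap allowed on open-label drug is 16 weeks. Starts at Week 36 (20) and Week 52 (36) exceed it; a start at Week 24 (8) does not.

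**5. First new scheduled values after dosing.** Haematology, chemistry and TB evaluation at PLUS 2 weeks, pregnancy test at PLUS 4, lipids and HbA1c at PLUS 12.

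**6. Planned size of the sirukumab-naive arms.** Arms D and E: 34 + 34 = 68 of 204 (68/204 = 33%). This is arm size only, not the number of late starters, which the documents do not give.

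**The case against.** The strongest textual objection is the general rule in Section 7 that a flare at any visit triggers the flare assessments in all the tables. Table 5's Flare column marks haematology, chemistry, lipids and HbA1c with no Week 16 limit. But the specific rule for the start visit points to Table 3, and Section 7 applies Table 5 only from PLUS 2 weeks. TB evaluation is absent from the Flare column in both tables, so the gap remains.

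Some points on weight do stand. Dosing is every two weeks and bloods recur at PLUS 2, so about one 100 mg dose precedes new samples. In Part A the baseline sample is drawn at the dosing visit and no text requires its result to be reviewed first, so the values in hand may be screening values up to about 6 weeks old, not far from the 8 weeks of a Week 24 start. Part A nevertheless has a same-day baseline sample and TB evaluation, which a late start lacks.

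Safeguards exist. QuantiFERON testing is called for if TB is suspected, contact with active TB triggers investigation and drug interruption, local laboratory tests are foreseen, and the start is at the investigator's discretion. All of these are discretionary or triggered; none is a scheduled check before this dose.

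Lipids, HbA1c and the pregnancy test matter less: the first two have no stopping limit in Table 7, and few subjects aged 50 or over need the third. Including them only matches what Table 4 already does at its start visit.

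**Conclusion.** The concern holds. Followed as written, the plan doses anyone starting open-label sirukumab after Part B Week 16 without the tests that the same plan schedules for a start at Part B entry. At the Week 24, 36 and 52 visits the last scheduled haematology, chemistry and TB evaluation are nominally 8, 20 and 36 weeks old; the last two exceed the plan's own longest on-drug haematology interval. This rests on Table 3 governing the start visit, as both Section 7 and Table 5 footnote 1 say, and on counting scheduled assessments only. It should be changed, since the safety gain costs little. The practical effect in this study depends on an unknown number of late starters, which may be small given the termination described in SAP Section 1.1.

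**What to change.** **Protocol**

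- In Table 5's Start column, add haematology, chemistry, lipids, HbA1c, TB evaluation and, where applicable, a urine pregnancy test, all before the first open-label dose.
- Limit Table 3 footnote 6 to flares that are not followed by open-label sirukumab.
- Require the TB questionnaire and urine test to be checked before dosing that day.
- For ANC, platelets and ALT/AST, state one rule: (a) a recent or local result is reviewed before the first dose, or (b) the same-day central-laboratory sample serves as a pre-dose baseline and early safety signal but does not gate dosing.

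**SAP Section 11**

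For late starters, use the start-visit sample as the laboratory baseline for change on open-label drug. Where there is none, use the last value before the first open-label dose and show its age. This fallback needs no new data, so it can be applied to what has been collected.

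**Cost**

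A few extra tubes at a visit that already draws blood for CRP and ESR, one questionnaire, a urine test for few subjects, table wording and a short SAP addition. Rule (a) may briefly delay the first dose in a flaring subject; corticosteroids remain available at the investigator's discretion.

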## 7.2. Screening and Critical Baseline Assessments

Cardiovascular medical history/risk factors (as detailed in the CRF) will be assessed at Screening.

The following demographic parameters will be captured: year of birth, sex, race and ethnicity.

Medical/medication/family history will be assessed as related to the inclusion/exclusion criteria listed in Section 5.

Procedures conducted as part of the subject's routine clinical management (e.g. chest radiograph taken up to 3 months prior to baseline) and obtained prior to signing of informed consent may be utilized for Screening or baseline purposes provided the procedure meets the protocol-defined criteria and has been performed in the timeframe of the study.

All subjects should be receiving prednisone treatment at Screening. Prednisone treatment must be initiated at Screening for subjects not currently receiving steroid treatment. Subjects should be reminded to discontinue any other prednisone or corticosteroid treatment and take only the prednisone study treatment. The prednisone dose for all subjects at Screening will be determined by the Investigator and may be adjusted based on the subject's disease status per investigator discretion. An increase in prednisone dose may be required for some subjects currently receiving therapy to stabilize their disease activity prior to randomization. Investigators may consider if higher doses of prednisone are warranted for subjects with visual manifestations. Subjects are required to have clinically stable GCA disease at baseline and able to participate in the blinded prednisone taper regimen in the opinion of the investigator. At Baseline (Randomization), doses must be within 20-60 mg prednisone for the starting dose when the pre-specified prednisone taper is initiated.

